7.8. Premature Discontinuation

Study is considered completed after the last scan of the day. Subjects may withdraw at any time. Subjects may be withdrawn at any time for safety concerns. Subjects who have any unanticipated problems (UPs) with the study procedures will be monitored until resolution of the symptoms.

7.9. Collection and Management of Tissue Specimens

Sample Preparation: N/A

Record Keeping and Monitoring: N/A

Sample Storage and Security: N/A

8. Study Measurements and Evaluations

List variables that will be abstracted from medical charts: Medical records will be reviewed to obtain previous FEV1 measurement and to confirm concomitant medications.

Describe screening evaluation: Vital signs, including heart rate, respiratory rate, temperature and blood pressure will be collected. Oxygen saturation levels will be noted, as well as breath sounds. A brief physical examination, including but not limited to the cervical lymph nodes, eyes, ears, nose, throat, cardiovascular and respiratory systems will be performed.

Describe how measurements will be taken:

Spirometry:

This test measures the volume of air that can be exhaled and the rate of airflow during exhalation after a maximal inhalation and is performed to American Thoracic Society (ATS) guidelines. Subjects will inhale as deeply as possible, then exhale as rapidly and completely as possible into the spirometer. Measurements obtained from each maneuver include the forced vital capacity (FVC), the forced expiratory volume in the first second (FEV1), the maximal mid-expiratory flow rate (FEF 25-75%) and the peak expiratory flow (PEF). The largest FVC and FEV1, from at least 3 acceptable trials, are selected for analysis; the flow rates are selected from the trial with the largest sum of FVC and FEV1.

Albuterol Inhalation:

The subject will be instructed on the proper use of MDI Inhaler, an approved device for inhalation of albuterol. The subject will use the inhaler to administer 4 puffs of albuterol.

MCC procedures:

Prior to each MCC study, a transmission Co57 scan will be performed to define the lung boundaries, to assign regions of interest, and to normalize these regions for lung volume differences. A rectangular phantom containing the radioisotope Co57 (< 25 mCi) will be placed in front (5cm) of the subject sitting with his/her back to the gamma camera for 30 seconds. The transmission scan has been used by us (e.g., 05-2358, 08-0795, 06-1016, 13-1605, 15-938) and others to provide a delineation of lung boundaries for generating the central (C) and peripheral (P) regions of interest (ROIs) used to assess initial particle deposition (C/P ratio) and subsequent clearance of the inhaled radio-aerosol [15-16]. Prior to the transmission scan on each study day, we will place 2 spot markers of Americium241 (0.9 microcurie (uCi) each, gamma 66 KeV) on the upper and lower back of each subject during scanning (both Tc99m-SC deposition/retention and Co57 transmission). With dual isotope imaging, these spot markers will allow alignment of images for more accurate determination of regional deposition/retention. These very low radiation sources have been obtained from commercially available home smoke alarms. The placement of these markers will be determined to be outside the lung field during the transmission scan. Their location will be marked in semi-permanent ink for later placement during Tc99m deposition/retention scans. The shielded side of this source will be placed/taped onto the subject's skin. Radiolabeled Tc99m-sulfur colloid will be delivered using a modified Pari-LC Star nebulizer (MMAD 9.5 um). This is a closed delivery system that produces 80 ml/sec air flow, and therefore limits the inspiratory flow rate to this value. While seated in front of a gamma camera subjects will perform single inhalations lasting ~10 seconds each from the delivery system and will exhale at 500 ml/sec (using feedback from a flow meter in the breathing circuit). Approximately 5 of these inhalation maneuvers will be required to deposit an adequate isotope dose to the lung. Subjects will be allowed to breathe normally (off the nebulizer) in between each inspiratory maneuver. Each volunteer will practice these maneuvers prior to the actual radio-aerosol inhalation to guarantee his/her proficiency. The activity of Tc99m-SC loaded in the nebulizer will be adjusted to provide an estimated 40 uCi deposited in the lung for the MCC/CC scan. Patients between the age 12-18 years old will receive ¼ of the adult dose to account for the smaller lung volume. A single crystal detector will be placed at the subject's back during inhalation to monitor dose to the lung. Total inhalation time should be less than 5 minutes in all cases. Immediately following isotope inhalation, the subject will gargle and drink water to clear activity that deposited in the mouth into the stomach. The subject will then (within a minute of final inhalation maneuver) be seated in front of a large-field-of-view gamma camera to begin acquiring consecutive 2 minute images. The first two-2 minute images will provide initial, time zero activity (i.e. 100% retention) followed by the same imaging at the start of every 10-minute period until 1 hour has passed to assess baseline MCC. Subjects will then inhale 4 puffs of albuterol from the MDI inhaler and consecutive 2 min imaging continues for the next hour to assess the effect of albuterol on MCC. PFTs will then be performed and subjects will cough a total of 30 times over a 30-minute period to assess CC by gamma imaging over that period. Finally, a static 15-minute image will be measured at 6 hours (±30 minutes) after the initial radio-aerosol deposition scan. (See table of procedures in section 4.1).

8.1. Outcome Measures for Evaluation of Feasibility / Tolerability

N/A

8.2. Outcome Measures for Evaluation of Efficacy

First estimates of the efficacy of SABA for accelerating MCC immediately in PCD subjects, will be obtained by comparing the baseline rate of MCC and the rate of MCC immediately after albuterol inhalation.

8.3. Outcome Measures for Evaluation of Safety

Vital signs are monitored throughout the study as needed, including heart rate, respiratory rate, temperature, and blood pressure.

We will assess vital signs at baseline, and then as needed when indicated by study physician.

9. Statistical Analysis Plans

9.1. Strategies that Apply to all the Specific Aims

To describe each measure of MCC by retention vs. time data set, the average % clearance (or 100* (1-Retention)) over the 0-60 and 60-120 min period of observation are computed (i.e. average of the 10 minute clearance values from 0 to 60 and 60-120 minutes). These computed values are signified as Ave60Clr and Ave120Clr respectively. Each calculated AveClr value utilizes all 10-minute data points, rather than simply reporting a clearance value at a single time, and represents the average clearance at the midpoint of each period of retention vs. time observation. 6 hour clearance is determined by (100* (1- 6 hour retention)) and provides an index of initial airway (6hr Clr) vs. alveolar (6hr retention) deposition that along with the central/peripheral (C/P) ratio provides regional deposition data that can be included as covariates in analysis of MCC comparisons between groups and within individuals.

Distributions of the outcomes is expected to be normal. We will plot the data in histograms and qqplot to evaluate any extreme datapoints or outliers. Their impact if any will be analyzed by performing the analysis with and without these datapoints.

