Aim 2: To characterize the effect of a short acting beta agonist (SABA) on MCC in PCD subjects with mutations in genes that are associated with mild or severe disease, and compare the 2 populations in terms of change in Average Clearance.

In aim 2, we will be measuring the effect of albuterol on MCC in PCD subjects. We will look at the change between Ave60Clear (before albuterol) and Ave120Clr (after albuterol) for each subject. Estimates of the means and standard deviations with associated confidence intervals will be reported for each group. Using paired t-tests, we will verify if the change is significantly different than 0. The difference between the 2 PCD groups will then be analyzed with an independent t-test. Age, gender and the initial deposition C/P will be added as covariates to PCD groups in a linear regression model on MCC.

As this is not a randomized crossover design nor a parallel-arm design, our proposed comparison pre- to post-albuterol is uncontrolled and cannot assess the efficacy of SABA. The goal of our study is to obtain first estimates of the immediate effect albuterol on MCC in a small, controlled population.

Aim 3: To characterize cough clearance in PCD subjects with mutations in genes that are associated with mild or severe disease, and compare the 2 populations in terms of change in Average Clearance.

We will compare cough clearance in PCD subjects with mutations associated with mild disease with PCD subjects with mutations in genes associated with more severe disease. Cough clearance will be measured as the change in retention between 120 and 150 min post deposition. This change between Ave120Clr and Ave150Clr will be tabulated for each PCD group in term of means and standard deviations with associated confidence intervals and compared to 0 using paired t-tests. The difference between the 2 PCD groups will then be analyzed with an independent t-test. Age, gender and the initial deposition C/P will be added as covariates to PCD groups in a linear regression model on MCC.

For all aims, all tests will be 2-sided, with $\alpha=0.05$. Tests with p values above 0.05 will be considered inconclusive.

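### As written, the Aim 2 change Ave120Clr-Ave60Clr is expected to exceed 0 with an inert drug, so 0 is not its no-effect value

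*Combined protocol and SAP*

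**What the plan says.** **Reference.** Section 8 (MCC procedures) fixes the starting point: "The first two-2 minute images will provide initial, time zero activity (i.e. 100% retention". For the rest of the first hour, the schedule is given as: "followed by the same imaging at the start of every 10-minute period until 1 hour has passed". Imaging continues for a second hour after albuterol, and no new reference is given.

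**Averages.** Section 9.1: "the average % clearance (or 100* (1-Retention)) over the 0-60 and 60-120 min period of observation are computed". These are Ave60Clr and Ave120Clr, and each "represents the average clearance at the midpoint of each period of retention vs. time observation". The 6-hour value uses the same form: "6 hour clearance is determined by (100* (1- 6 hour retention".

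**Aim 2 analysis (section 9.3).** "We will look at the change between Ave60Clear (before albuterol) and Ave120Clr (after albuterol) for each subject". Then: "Using paired t-tests, we will verify if the change is significantly different than 0". An independent t-test compares mild with severe, followed by a regression on age, gender and C/P. The Synopsis and section 4.1 (Outcome Measures) use the same difference. Section 9.3 calls the comparison "uncontrolled and cannot assess the efficacy of SABA".

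**Other descriptions of the effect.** Section 8.2 compares a rate before albuterol with a rate after it. Section 9.6 expects Ave60Clr of 14.3 (SD 7.2) in healthy, 3.6 (SD 2) in mild and 0.5 (SD 0.25) in severe subjects. It has albuterol doubling the mild value to 7.2 (SD 4), still labelled Ave60Clr, with no response in severe. The expected results in section 9.3 predict the same pattern.

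**The concern.** Clearance measured from a single time zero accumulates. Its average over the second hour exceeds its average over the first whenever material is still clearing, whatever the drug does. A paired test against 0 then largely tests whether clearance continued. A faster-clearing group also tends to accumulate more in the second hour, so the mild-versus-severe comparison can show a larger albuterol change in the mild group when there is none.

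At stake are the secondary outcome and the plan's first estimates of the immediate albuterol effect. Those estimates and their confidence intervals would consist mostly of ordinary clearance over time, and would agree with the stated hypothesis.

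**Working it through.** **1. The plan's own figures.** 0.25 x 14.3 = 3.6, 2 x 3.6 = 7.2 and 10 x 1.2 = 12 all reproduce. Power for 3.6 to 7.2 with SDs 2 and 4 at n=10 depends on a pre-post correlation that is not given: 0.62 at r=0, 0.72 at r=0.25, 0.83 at r=0.5. The stated n can therefore be neither confirmed nor refuted.

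**2. Which images enter each average.** The flow sheet in section 4.1 allots 64 and 54 minutes to the two scans. With 4 minutes per imaging point (two 2-minute images), 64 = 60 + 4 and 54 = 50 + 4. This fits images at 10-60 and 70-120 min, the main grid here. Section 8 can also be read as 0-50 and 60-110 min.

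**3. No-drug change, linear clearance.** Let C(t) = s x t. The mean time is 35 min on 10-60 and 95 min on 70-120.
- Mild: s = 3.6/35 = 0.1029; Ave120Clr = 95 x 0.1029 = 9.8; change +6.2.
- Severe: s = 0.5/35 = 0.0143; Ave120Clr = 1.36; change +0.86.

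**4. No-drug change, curved clearance.** Let C(t) = P x (1 - exp(-kt)), where P is the percentage of the deposit that can clear. Choose k so that the first-hour mean is 3.6 or 0.5, and leave k unchanged after 60 min.

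| P (%) | Mild Ave120Clr | Mild change | Severe change |
|---|---|---|---|
| 100 (first-order) | 9.50 | +5.90 | +0.85 |
| 40 | 9.09 | +5.49 | +0.84 |
| 20 | 8.43 | +4.83 | +0.83 |
| 15 | 7.99 | +4.39 | +0.82 |
| 10 | 7.15 | +3.55 | +0.80 |

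On the 0-50/60-110 grid, including the linear case, mild is +4.5 to +8.6 and severe +1.1 to +1.2. A healthy mean of 14.3 requires more than 14.3% to be clearable. If PCD deposits are at least as clearable (an assumption), 15% is near the lower end.

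**5. Fast levelling-off.** With a 20-minute half-life in both groups, the ratio of second-hour to first-hour average is 1.475 on the main grid, so mild is 3.6 x 0.475 = +1.7. Averaging 0-60 and 60-120 min gives a ratio of 1.701 and +2.5. With a 10-minute half-life the mild change on the main grid is only +0.7. With a common P, the mild-over-severe order reverses below about 4.4% clearable.

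**6. Rejection with no drug effect.** Simulation with n=12 per group, the section 9.6 means and SDs, P from 10% to 100%, and assumed independent image noise:
- mild paired test: 95-100% at noise SD 0.5-4;
- mild versus severe: 94-100% at SD up to 2, 53-98% at SD 4;
- severe paired test: 19-100%.

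In a separate power calculation for the plateau curves, with noise SD 2 placed on the change itself, the mild paired and between-group rates are 0.68 and 0.37 at a 20-minute half-life, and 0.19 and 0.11 at 10 minutes.

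**7. Which scale section 9.6 fits.** Under first-order clearance with the mild rate doubled after 60 min, a value re-based at 60 min averages 7.0, close to the plan's 7.2. On the time-zero scale, Ave120Clr is 9.5 with no drug and 12.7 with the doubled rate. Sections 8.2 and 9.6 therefore fit an hour-specific measure, while sections 8, 9.1 and 9.3 define a cumulative one.

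**The case against.** **The plan already calls the comparison uncontrolled.** It does, and that properly limits claims of efficacy. It does not say that the difference is positive by construction, and the test against 0 and the group comparison remain. Healthy controls follow the same protocol, so no albuterol-free second hour is described, and the listed covariates do not include baseline clearance.

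**The investigators may intend to re-zero at 60 minutes.** This stands in part. No sentence excludes it, and sections 8.2 and 9.6 point that way. A reader might infer that the trial will certainly report a spurious albuterol effect. The documents support less: followed literally, the plan does so, and the intended scale is unsettled.

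**The sizes rest on assumed curves and noise.** This stands. Fast plateaus fall below the main range, and no section supports a floor of 10% clearable. The direction and the non-zero null need only continuing clearance; the size, and the mild-over-severe order, need more.

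**Re-basing has problems of its own.** This also stands. Redefining Ave120Clr itself would damage Aim 3: under first-order clearance, with clearance at 124 min as the later value, the mild no-cough difference becomes about +8.6 instead of +2.7. Re-basing also loses power when the clearable fraction is limited. The fix allows for both.

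**Conclusion.** The concern holds for Aim 2. As written, Ave120Clr-Ave60Clr has a positive expectation with an inert drug wherever clearance continues, so 0 is not the no-effect value. On 10-60/70-120 min images with at least 10% clearable, the no-drug change is about +3.6 to +6.2 in mild and +0.8 to +0.9 in severe; with a 20-minute half-life the mild change is about +1.7 to +2.5. In these cases the planned mild and between-group tests reject far more often than 5%, in the predicted direction. The excess shrinks as clearance nears exhaustion within the first hour.

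The sign and the wrong null are secure on the plain reading. The exact sizes are not, because curve shape, clearable fraction, image grid and noise are not in the documents.

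Two stronger readings are not supported. The primary outcome is not affected, since Ave60Clr uses only the first hour. Nor does mild exceed severe under every curve; that needs similar shapes and clearance that is not close to exhausted.

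**What to change.** 1. Reconcile sections 8, 8.2, 9.1, 9.3 and 9.6 by stating the reference image and the image grid for each average.
2. Keep Ave120Clr on the time-zero scale, so that Aim 3's Ave150Clr-Ave120Clr is unchanged.
3. For Aim 2, add a separately named second-hour value, 100 x (1 - R(t)/R(60)) averaged over 70-120 min, where R(60) is the 60-minute pre-albuterol image. Compare it with Ave60Clr averaged over 10-60 min. Use this change in the Synopsis, section 4.1 (Outcome Measures) and section 9.3, and restate section 9.6 on the same scale.
4. Report the change per group and between groups as estimates with confidence intervals, described as uncontrolled. State that 0 is the no-effect value only under first-order clearance of the whole deposit, and that the no-effect value is negative if the clearable fraction is limited. Do not read a p-value as a drug effect or as its absence. An analysis scaled to 6-hour clearance may be shown descriptively only, since that image follows both albuterol and directed coughing.

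**Cost.** This is wording only, on images already planned, but the downsides should be disclosed. The R(60) image adds noise. The no-drug mean of the re-based change in the mild group, over the 3.6 (SD 2) distribution, is +0.3 if linear, 0 if first-order, and -0.5, -1.2, -1.7 and -2.4 at 40, 20, 15 and 10% clearable. Power also falls. For a true doubling of the mild rate (simulated, n=12, image noise SD 1/2), an increase is detected in about 100/94% of trials at 100% clearable, over 99/77% at 40%, 29/12% at 20% and about 1-2% at 15%. At 10% no increase is detected, and a false decrease appears in 55/31%. A null or negative result therefore cannot be read as no response.

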4.1 Treatment Design

Type of Design: Open label; two group study with healthy controls

Screening/Baseline: Participants will undergo a general medical screening visit to include vital signs, physical exam and pregnancy test (if applicable), then proceed with spirometry.

Intervention/Treatment

Participants will inhale aerosolized radiolabeled sulfur colloid ($Tc99m$ -SC) and will undergo gamma scintigraphy to measure mucociliary and cough clearance (MCC/CC) of the radiolabeled particles from the airways in both groups. During the first hour of MCC imaging patients will attempt to avoid coughing. Patients will then inhale 4 puffs of albuterol (90 mcg/puff via metered dose inhaler (MDI) with spacer) to assess the effect of beta-adrenergic stimulation on MCC over the second hour of MCC

imaging. After the two hours of MCC imaging patients will perform spirometry and directed coughing over a 30 minute period during which CC will be measured, again by gamma scintigraphy. Subjects will then rest (app 3.5 hours) and be scanned for 15 minutes at 6 hour \pm 30 minutes post initial MCC/deposition scan.

Table of procedures

| PCD MCC/CC study flow sheet | minutes needed | cumulative min |
|---|----------------|----------------|
| 1 Vital signs, PE,pregnancy test, PFT | 30 | 30 |
| 2 Put Americium fiducial markers on | 5 | 35 |
| 2 Co57 Transmission scan | 5 | 40 |
| 3 Background scan | 15 | 55 |
| 4 Radioaerosol inhalation | 5 | 60 |
| 5 MCC scan (no cough) | 64 | 124 |
| 6 Albuterol MDI (4 puffs with spacer) | 6 | 130 |
| 7 MCC scan post albuterol | 54 | 184 |
| 8 PFT and directed coughing (30 coughs including any spontaneous induced by PFTs) | 20 | 204 |
| 9 CC scan post PFT/cough | 4 | 208 |
| 10 Rest until final scan 6 hours after beginning of #5 | 210 | 418 |
| 11 6 hour post initial radioaerosol MCC scan | 15 | 433 |

Unscheduled Visits: There is no expectation for unplanned visits. Subjects will simply be rescheduled if they have a change in health.

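### The Aim 2 albuterol contrast compares cumulative clearance at two times, and most likely counts a pre-dose image as post-dose, so it rises without any drug effect

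*Combined protocol and SAP*

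**What the plan says.** **Measure.** Section 9.1 computes clearance as 100*(1-Retention) and takes the "average of the 10 minute clearance values from 0 to 60 and 60-120 minutes". It adds that "Each calculated AveClr value utilizes all 10-minute data points" and that the result "represents the average clearance at the midpoint of each period of retention vs. time observation". Section 8 (MCC procedures) fixes the reference: "The first two-2 minute images will provide initial, time zero activity (i.e. 100% retention". Nothing in 8 or 9.1 resets that reference at the time of dosing.

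**Contrast.** Section 9.3, Aim 2: "We will look at the change between Ave60Clear (before albuterol) and Ave120Clr (after albuterol) for each subject". The change is tested against zero with a paired t-test in each group and then compared between the two PCD groups. Section 8.2 describes the aim as comparing the rate of clearance at baseline with the rate just after albuterol.

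**Timing.** Section 8 describes the first-hour imaging as "followed by the same imaging at the start of every 10-minute period until 1 hour has passed to assess baseline MCC". The flow sheet in 4.1 lists "5 MCC scan (no cough) | 64 | 124" (minutes needed, cumulative minutes). The dosing row, "Albuterol MDI (4 puffs with spacer"), takes 6 minutes, and the post-albuterol scan takes 54.

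**Expected response.** Section 9.6 expects the mild group to go from 3.6 ± 2% to 7.2 ± 4%, a change of 3.6 points.

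**The concern.** The contrast is meant to show what changes after albuterol. Two features of the definition prevent that.

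1. Each post-albuterol value still contains everything cleared in the first hour. A subject whose clearance rate never changes will have a higher average in the second hour than in the first.
2. The averaging window opens at 60 minutes, but dosing starts at 64. If the 60-64 minute image belongs to the window, a pre-dose value is averaged into a measure labelled as after albuterol.

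At stake is the secondary outcome. The paired test could be significant, and the stated doubling could appear to be met, with no drug effect. The between-group comparison of changes could largely repeat the baseline difference that Aim 1 already measures.

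**Working it through.** **1. Image times (flow sheet, 4.1).** The first scan starts at cumulative minute 60 and ends at 124, which is 0-64 on the scan clock. Dosing runs to 130 (64-70) and the second scan to 184 (70-124). With 4-minute images (two of 2 minutes) every 10 minutes, the images start at 0, 10, ..., 60 before dosing and 70, 80, ..., 120 after it. The 60-64 minute image is wholly pre-dose. The 70-minute image starts as the dosing step ends.

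**2. Is the 60-minute image in Ave120Clr?** Section 9.1 does not say which window owns it. The points 60, 70, ..., 120 average 90, the midpoint of the period; 70, ..., 120 average 95. The midpoint sentence therefore favours inclusion.

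**3. Change with no drug effect.** Inputs: Ave60Clr = 3.6 (9.6). Assumption: cumulative clearance C(t) = r·t, with constant r.

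| Baseline images | Mean time | r = 3.6/mean time | Ave120Clr = 90r | Change |
|---|---|---|---|---|
| 0..60 | 30 min | 0.120 | 10.8 | +7.2 |
| 10..60 | 35 min | 0.1029 | 9.3 | +5.7 |

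Both values of Ave120Clr exceed the 7.2 that 9.6 treats as a response. If clearance slows exponentially to a plateau (assumed half-times 30-120 minutes), the no-drug Ave120Clr is 6.0 to 9.4, a change of +2.4 to +5.8.

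**4. What this does to the tests.** At constant clearance each subject's change is a fixed multiple of Ave60Clr, so mean/SD of the change equals 3.6/2 = 1.8. A paired t-test with n = 10 and standardised effect 1.8 rejects with probability 0.999 (noncentral t, two-sided 0.05, no measurement noise), with no drug effect. For the severe group (Ave60Clr 0.5 in 9.6) the no-drug change is 0.5 × 55/35 = 0.8 to 0.5 × 60/30 = 1.0. The mild-severe difference in change is then about 5.66 - 0.79 = 4.9 to 7.2 - 1.0 = 6.2, again without a drug effect.

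**5. Dilution from the 60-minute image.** Assumption: albuterol adds a constant extra rate d from minute 70. Extra clearance at 60, 70, ..., 120 is 0, 0, 10d, 20d, 30d, 40d, 50d.
- Mean over 60..120: 150d/7 = 21.4d.
- Mean over 70..120: 150d/6 = 25.0d.
- Ratio 21.4/25.0 = 0.857, a loss of 14%.

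The loss is the same with onset at 64 minutes (26.57/31.0) or 67 minutes (24.0/28.0), since the 60-minute image adds a zero to the sum and one to the count. If albuterol doubles the rate (d = r), the lost amount is 3.57 min × 0.1029 to 0.120 per min, or about 0.4 points. The accumulation in step 3 is far larger.

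**6. The corrected contrast, no drug effect.** With the 60-64 minute image as 100%, post clearance is r(t-60)/(1-60r/100), and the mean elapsed time over 70..120 is 35 minutes.
- Baseline 10..60: 3.60/0.9383 = 3.84, change **+0.2**.
- Baseline 0..60: 4.20/0.928 = 4.53, change +0.9.
- With 80..120 (40 minutes elapsed): +0.8 and +1.6 respectively.

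Only 70..120 against 10..60 matches elapsed time. With a doubled rate from minute 70, the drug part on this scale is 25.0 × 0.1029/0.9383 = 2.7 points over a no-drug change of 0.2. Under the plan's definition (10..60 and 60..120) it is 21.43 × 0.1029 = 2.2 over a no-drug change of 5.7.

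**The case against.** **The plan already disclaims efficacy.** Section 9.3 says the pre/post comparison is uncontrolled and cannot assess the efficacy of the SABA. That stands, and it limits the consequence. But the same paragraph sets the goal of a first estimate of the immediate effect, and this contrast is not an estimate of it even descriptively.

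**The intent may be a per-period measure.** Section 8.2 speaks of rates, and 9.6 labels the post-albuterol value as an Ave60Clr. If the analysts re-reference at 60 minutes in practice, the accumulation largely disappears. Section 9.1 does not say so, and its definition gives the cumulative value.

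**The 60-minute image may not be shared.** Section 8 assigns the first-hour images to baseline, and the flow sheet labels the later scan as post-albuterol. If Ave120Clr uses 70..120 only, the 14% goes away. The accumulation does not: with baseline 10..60 the no-drug change is then +6.2 (9.77 - 3.6).

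**A stronger reading.** A reader might infer from the timing that the planned contrast understates albuterol's effect. The documents do not support that. Only the drug-attributable part is diluted, while the net contrast is pushed upward. A reader might also put the dilution at 29% (21.4d against 30.0d). That requires dropping the 70-minute image too, and on the flow sheet that image starts once dosing has ended. Averaging 80..120 against the existing baseline would also give the post side more elapsed time and a spurious rise.

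**The definition has other users.** Ave120Clr is also the reference for Aim 3, and 9.6 states the response on its scale. This stands and shapes the fix.

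**Conclusion.** The concern holds in this form: the Aim 2 contrast, as defined, does not isolate the post-dose period. It is positive with no drug effect, by about +5.7 to +7.2 points at constant clearance when Ave60Clr is 3.6, against a planned response of 3.6. Its most likely window also counts a pre-dose image, which cuts the drug-attributable part by about 14%. The first effect dominates, so the net bias is upward.

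The sizes rest on assumptions. The documents give no time course of clearance and no onset of albuterol action, and inclusion of the 60-minute image is the likely reading rather than an explicit statement. The direction of the accumulation follows from the definition for any subject who goes on clearing.

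**What to change.** In 9.1, list the images that enter each average. For Aim 2:

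- Assign the 60-64 minute image to the baseline side only, and use it as the reference (100%) for the post-albuterol period.
- Average post-albuterol clearance over the 70-120 minute images and compare it with baseline clearance averaged over the 10-60 minute images. Mean elapsed time is then 35 minutes on each side, and the contrast compares rates as 8.2 intends.
- Allow an 80-120 minute average only as a sensitivity analysis, with a baseline window of matching elapsed time.
- Restate the expected response in 9.6 on the new scale.

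Keep the time-zero-referenced values for Aim 3.

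Cost: no new images, visits or participants, and text changes in 9.1, 9.3 and 9.6. Each average has one fewer image, and a single reference image adds some noise.

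One limit should be stated in 9.3. If clearance slows naturally, the corrected contrast is negative without a drug effect. With an assumed half-time of 60 minutes, second-hour gains are half of first-hour gains: 1.8/0.944 = 1.9 against 3.6, or -1.7. Without a control, no definition of the measure removes that.
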